4.6. Benefit:Risk Assessment

Summaries of findings from non-clinical studies conducted with GSK3342830 can be found in the IB [GSK Document Number [2015N255155_00](#)].

Section [4.6.1](#) outlines the risk assessment and mitigation strategy for this study.

4.6.1. Risk Assessment

Potential Risk of Clinical Significance	Summary of Data/Rationale for Risk	Mitigation Strategy
Investigational Product (GSK3342830)		
Death in preliminary monkey cardiovascular study	
 • Preliminary monkey cardiovascular study: 
 • No effect on corrected QT (QTc) 
 • 1 death • 1/3 animals, single dose escalation design with 1-week washout; 4th dose at 1000 mg/kg • Animal died at 2.5 hours post-dose • No clear etiology • No similar findings in definitive cardiovascular study • 26 animals now dosed at and above 1000 mg/kg and at longer durations (4 weeks) without major adverse findings 	
 • Conduct study in inpatient clinical unit for first time in human (FTIH) • Normal vital signs on study entry • Frequent vital signs over the dosing interval • QTc <450 msec • 12-lead electrocardiograms (ECGs) across the initial exposure • Telemetry monitoring for Parts 1 and 3 and initial doses in Part 2
Blood pressure (BP), heart rate, and body temperature changes in monkey cardiovascular study	
 • Blood pressure: 
 • Maximum excursion of 29 mm Hg at 1000 mg/kg • Heart rate: 
 • Maximum excursion of 16 beats per minute at 1000 mg/kg • Body temperature: 
 • 0.5°C decrease at 1000 mg/kg 	
 • Conduct study in inpatient clinical unit for FTIH • Starting dose free C_{max} margin: approximately 26× • C_{max} at highest planned dose (6000 mg) similar to (1.1×) C_{max} of the no observed effect level (NOEL) dose (250 mg/kg) • Normal vital signs on study entry • Frequent vital signs over the dosing interval • 12-lead ECGs across the exposures • Telemetry monitoring for Parts 1 and 3 and initial doses in Part 2 • Blood pressure and heart rate stopping criteria: 
 • Systolic BP >160 mm Hg for >1 hour • Diastolic BP >100 mm Hg for >1 hour • Heart rate >120 beats per minute for >1 hour

Potential Risk of Clinical Significance	Summary of Data/Rationale for Risk	Mitigation Strategy
Renal findings	
 • Kidney: hyaline droplets in proximal tubules, weight increase in both species 
 • Hyaline droplets associates with absorption and secretion of the cephem antibiotics in lysosome • No degenerative changes • Probably mixture of drug and protein (stimulation of lysosomal turnover) • Accompanied by increases in urinary N-acetyl-β-D-glucosaminidase (exploratory biomarker of lysosomal enzyme) at all doses and slight change in urinary albumin at 2000 mg/kg (relevance unclear) 	
 • Inclusion/Exclusion 
 • Healthy subjects • Serum creatinine greater than the upper limit of normal (ULN) • Estimated glomerular filtration rate (eGFR) <90 mL/min/1.73 m² as calculated by the Chronic Kidney Disease Epidemiology Collaboration formula • Albumin to creatinine ratio (ACR) ≥0.03 mg/mg • Urinalysis negative for blood/protein • Monitor: 
 • Serum blood urea nitrogen, creatinine, eGFR, electrolytes, urinalysis • ACR during the study • Criteria to pause Part 1 progression or interrupt Part 2 dosing 
 • Creatinine change >0.3 mg/dL without alternative cause • New blood in urinalysis confirmed by microscopy without alternative cause • ACR ≥0.03 mg/mg
Injection site reactions	
 • Local irritation 
 • Gross: discoloration, hardening, wound, thrombosis • Histology: ulcer, perivascular/vascular inflammation, thrombus (1000/2000 mg/kg/day; rats and monkeys) • Considered due to high osmolality of the dosing formulations 	
 • Reduced osmolality preparation • Monitor injection site including proximal limb for vascular change

Potential Risk of Clinical Significance	Summary of Data/Rationale for Risk	Mitigation Strategy
Hematologic findings	
Red Blood Cell (RBC) related changes
 
 • Decreases in RBC count, hemoglobin (Hgb), hematocrit (Hct; 2000 mg/kg/day in males and females) 
 • Peaked at Week 2 (-10% to -20% versus pre-dosing values) • Accompanied by increase in reticulocytes • RBC findings considered secondary to: 
 • Ongoing inflammation from infusion site reactions (above) • Contribution from high osmolality infusion • Hemolysis, iron depletion (catechol) or other direct mechanism of drug not considered present • Evidence of recovery by end of follow-up 
Other hematologic findings
 
 • Findings considered secondary to ongoing inflammation at the infusion site • Increases in neutrophils and concomitant decreases in lymphocyte % • Decreased fibrinogen • Prolongation of activated partial thromboplastin time • Decreases in albumin and albumin/globulin ratio • Increase in total protein (due to globulin increase) • development of iliac lymph node germinal center • Findings were reversible in follow-up 	
 • Reduced osmolality infusions • Normal white blood cell (WBC) count, Hgb, Hct, and platelets on study entry • Follow for signs or symptoms of anemia • Follow regular clinical labs (WBC, Hgb, Hct, reticulocyte count, and platelets) 
Stopping criteria
 
 • Hemoglobin ≤ 9.9 g/dL (99 g/L) • White blood cell $\leq 1999/\text{mm}^3$ ($1.910 \times 10^9/\text{L}$) • Platelets $\leq 99.999 \times 10^9/\text{L}$
Increased tidal volume in rat respiratory study	
 • Only at high dose (2000 mg/kg) • 22.9% at 30 minutes after completion of infusion • Changes considered to be minimal 
 • Magnitude within the range of physiological changes • No changes were seen in minute volume • Not statistically significant • May reflect high individual variability 	
 • Conduct study in inpatient Phase I clinical unit • Frequent vital sign capture during study • 6000 mg maximum dose maintains 2.1\times margin relative to the NOEL of 1000 mg/kg

Potential Risk of Clinical Significance	Summary of Data/Rationale for Risk	Mitigation Strategy
Serotonin (5-HT)-3 in vitro binding assay	
 • “Moderately” positive with 39% effect at 100 mmol (78 µg/mL) • High dose Cmax will reach similar concentration • No clear in vivo correlation from toxicology studies 
 • Possible BP effect in monkey cardiovascular study • Poor central nervous system penetration (approximately 3% blood) 	
 • Precautions c/w those indicated to mitigate the BP effect seen in monkey cardiovascular study • Enroll healthy subjects not on medications to avoid additive arrhythmogenic potential
Other		
Neurologic findings (seizures)	
 • Known risk (seizures) for some β-lactams and cephalosporins • Seen pre-clinically with lead compound • No adverse findings to 2000 mg/kg/ day × 4 weeks in rats or monkeys • Central nervous system administration study in rats negative 	
 • Specifically assess for negative history of seizures in past medical history at screening • Close monitoring during infusion in an acute care setting
Rash/Dermatologic toxicity	
 • Rash is a common adverse event (AE) of β-lactam antibiotics. Range of manifestations and severity from mild morbilliform drug eruption to hives, Erythema multiforme (EM), Stevens-Johnson syndrome (SJS) and toxic epidermal necrolysis (TEN) in rare cases 	
 • Exclude individuals with history of rash to penicillins or cephalosporins • Exclude individuals with history of EM/SJS/TEN to any medication • Close monitoring • Discontinuation criteria 
 • Any rash of Grade 3 or greater severity • Any rash characterized by: 
 • Hives • Concomitant fever or other symptoms suggesting systemic manifestations • Blistering • Ocular or genital involvement • Access to standard interventions (antihistamines, steroids if indicated, intensive care unit/burn unit care in worst case)
Anaphylaxis/hypersensitivity	
 • Common to all β-lactam antibiotics 
 • Approximately 10% cross reaction between cephalosporins and penicillins • Guinea pig immunotoxicity model negative 	
 • Conduct study in inpatient Phase I clinical unit • “Crash” cart availability • Exclude subjects with history of penicillin allergy

Potential Risk of Clinical Significance	Summary of Data/Rationale for Risk	Mitigation Strategy
Clostridium difficile (C. difficile) colitis	
 • A general risk with all antibiotics • Cephalosporins generally considered moderate to high risk presumably due to broad effects on gut microbiome • No anaerobic activity may reduce propensity for C. difficile overgrowth 	
 • Exclude subjects with a history of C. difficile colitis • Site chosen with experience in antibiotics studies • Importance of infection control procedures will be raised with the site
Liver findings	
 • No adverse findings to 2000 mg/kg/day × 4 weeks in rats or monkeys • Increase in liver weight (monkey) 
 • Mechanisms unclear • No corresponding alanine aminotransferase (ALT) or aspartate aminotransferase (AST) or histopathological change 	
 • Normal liver biomarkers on study entry with negative history of liver disease in past medical history • Frequent assessment of symptoms suggesting liver injury (nausea, vomiting, abdominal pain, etc.) • Frequent assessment of liver injury biomarkers (ALT, AST, total bilirubin, direct bilirubin, alkaline phosphatase) • Defined GSK liver stopping criteria
Catechol side chain binds free iron	
 • Catechol side chain binds free iron (part of the monoamine oxidase) 	
 • Normal Hgb and Hct on study entry • Monitor Hgb and Hct with stopping criteria as above • Monitor iron binding studies (serum iron, ferritin, total iron binding capacity, reticulocytes)
Candidiasis (vaginal, oral thrush)	
 • A common AE of exposure to broad spectrum antibiotics 	
 • Monitor clinically • Discontinue GSK 830 may be needed for treatment • Treat with topical antifungal medication as needed

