Details of the required monitoring including the specific plan to monitor for and manage likely AEs or adverse reactions, and individual subject withdrawal/stopping criteria and the procedures and responsibilities for modifying or stopping the trial, if necessary, are specified in Section 4.6 and Section 5.4, respectively.

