11. History of hypersensitivity attributed to β -lactam antibiotics (including cephalosporin, carbapenem, or penicillin antibiotics) or other drugs, a history of multiple antibiotic intolerances, or a history of serious adverse drug reactions.
12. Sensitivity to poison ivy or other catechol-related hypersensitivity (e.g., mango allergy).
13. History of sensitivity to heparin or heparin-induced thrombocytopenia.
14. History of latex allergy.
15. History of sensitivity to any of the study treatments or components thereof, or a history of drug or other allergy that, in the opinion of the investigator or medical monitor, contraindicates participation in this study.

DIAGNOSTIC ASSESSMENTS AND OTHER CRITERIA

16. Presence of hepatitis B surface antigen or positive hepatitis C antibody test result at screening or within 3 months before the first dosing day in this study.
17. Serum creatinine >ULN.
18. Glomerular filtration rate <90 mL/min/1.73m² as calculated by the Chronic Kidney Disease Epidemiology Collaboration formula (See [Appendix 11](#)).
19. Albumin to creatinine ratio (ACR) >0.03 mg/mg. In the event of an ACR above this threshold, eligibility may be confirmed by a second measurement.
20. Urinalysis positive for blood without other cause identified.
21. A positive pre-study drug or alcohol screen.
22. A positive test for human immunodeficiency virus antibody at or before screening.
23. Where participation in the study would result in donation of blood or blood products in excess of 500 mL within a 56-day period.
24. The subject has participated in a clinical trial and has received an investigational product within the following time period before the first dosing day in this study: 30 days, 5 half-lives or twice the duration of the biological effect of the investigational product (whichever is longer).
25. Exposure to more than 4 new chemical entities within 12 months before the first dosing day in this study.
26. Exclusion criteria for screening and baseline 12-lead ECG (a single repeat is allowed for eligibility determination):

	Males	Females
Heart rate	<40 and >100 beats per minute	<50 and >100 beats per minute
PR interval	<120 and >220 msec	
QRS duration	<70 and >120 msec	
QTcB or QTcF interval	>450 msec	
QTcB = corrected QT interval using Bazett's formula, QTcF = corrected QT interval using Fridericia's formula.		

- a) Evidence of previous myocardial infarction (does not include ST segment changes associated with repolarization).

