5.4. Withdrawal/Stopping Criteria

The following actions must be taken in relation to a subject who fails to attend the clinical unit for a required study visit:

- The site must attempt to contact the subject and re-schedule the missed visit as soon as possible.
- The site must counsel the subject on the importance of maintaining the assigned visit schedule and ascertain whether or not the subject wishes to and/or should continue in the study.
- In cases where the subject is deemed ‘lost to follow up’, the investigator or designee must make every effort to regain contact with the subject (where possible, 3 telephone calls and if necessary a certified letter to the subject’s last known mailing address or local equivalent methods). These contact attempts should be documented in the subject’s medical record.
- Should the subject continue to be unreachable, only then will he/she be considered to have withdrawn from the study with a primary reason of “lost to follow up”.

A subject may withdraw from study treatment at any time at his/her own request, or may be withdrawn at any time at the discretion of the investigator for safety, behavioral, or administrative reasons. If a subject withdraws from the study, he/she may request destruction of any samples taken, and the investigator must document this in the site study records.

This protocol defines several clinical laboratory values, 12-lead ECG values, vital sign values, and additional safety criteria that, if observed and confirmed, mandate cessation of drug dosing and further evaluations. Any laboratory result that meets the stopping criteria should be repeated once to confirm the value before the subject is withdrawn from the study.

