5.4.3. Renal Stopping Criteria

Study treatment will be discontinued for a subject who meets any of the following criteria:

- Persistent (confirmed on recheck) elevation of serum creatinine (>0.3 mg/dL) without an alternative cause identified
- Albumin to creatinine ratio ≥ 0.03 mg/mg
- New blood in urinalysis confirmed by microscopy without an alternative cause identified

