Other Screening Tests	
 • Human immunodeficiency virus • Hepatitis B surface antigen • Hepatitis C antibody • Follicle-stimulating hormone and estradiol (as appropriate) • Alcohol, cotinine, and drug screen (to include at minimum: amphetamines, barbiturates, cocaine, opiates, cannabinoids and benzodiazepines) • β-human chorionic gonadotropin pregnancy test (if female of child-bearing age; serum at screening and urine at Day -1 and follow-up) 			

ACR = albumin to creatinine ratio, ALT = alanine aminotransferase, AST = aspartate aminotransferase, KIM-1 = kidney injury molecule 1, MCH = mean corpuscular hemoglobin, MCHC = mean corpuscular hemoglobin concentration, MCV = mean corpuscular volume, NGAL = Neutrophil gelatinase-associated lipocalin, RBC = red blood cell, TIBC = total iron binding capacity, WBC = white blood cell
 
Footnotes are on the next page.
				

NOTES:

1. In Parts 1 and 3, analyzed on Day –1 and at Follow-up visit. In Part 2, analyzed on Day –1, Day 5, Day 15, and at Follow-up visit.
2. Blood samples will be collected on Day –1, predose (at least 1 hour before dosing) on Days 5, and 15, and at Follow-up visit..
3. Details of Liver Chemistry Stopping Criteria and Required Actions and Follow-Up Assessments after liver stopping or monitoring event are given in Section 5.4.1, Appendix 2, and Appendix 3.
4. The ACR on urine albumin and creatinine will be determined using the first morning void urine at Screening and Follow-up visit for all subjects in both parts of the study. In addition, the ACR will be determined on Day 2 in Parts 1 and 3, and Days 5 and 15 in Part 2. Screening ACR may be performed on urine during the screening visit. Subjects should be provided a sterile urine transport container and instructions on how to collect a first void urine at home for screening. In the event a subject fails by ACR, the subject should be contacted to bring back first void urine for recheck. For the Follow-up visit, subjects must be provided a sterile urine transport container on discharge from the clinical unit and instructed to bring back the first morning void urine on the day of their return Follow-up visit.
5. An aliquot of the remaining urine samples will be banked and may be analyzed for NGAL and KIM-1 after the end of the study if a clinical signal is detected. Instructions for collection and storage of these urine samples are included in the Study Reference Manual.

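### Section 5.2 admits an albumin-to-creatinine ratio of exactly 0.03 mg/mg, which Section 4.6.1 excludes and Section 5.4.3 stops on

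*Protocol*

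**What the plan says.** Four parts of the protocol set the ACR rules.

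- **Entry, Section 5.2 item 19.** The exclusion is "Albumin to creatinine ratio (ACR) >0.03 mg/mg". A second measurement may confirm eligibility, but only for a result above the threshold.
- **Entry and management, Section 4.6.1, renal row.** The entry criteria include "Albumin to creatinine ratio (ACR) ≥0.03 mg/mg". The same limit appears again under "Criteria to pause Part 1 progression or interrupt Part 2 dosing", beside a creatinine change above 0.3 mg/dL and new microscopy-confirmed blood in urine.
- **Stopping, Sections 5.4 and 5.4.3.** Study treatment is discontinued for a subject with "Albumin to creatinine ratio ≥ 0.03 mg/mg". Section 5.4 adds: "Any laboratory result that meets the stopping criteria should be repeated once to confirm the value before the subject is withdrawn from the study".
- **Schedule, Section 7.3.7, Table 7 note 4.** ACR is measured at screening and follow-up in all subjects. "In addition, the ACR will be determined on Day 2 in Parts 1 and 3, and Days 5 and 15 in Part 2". No other ACR is scheduled before the first dose.

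The SAP repeats the ACR schedule in its Appendix 1 and sets no ACR threshold of its own.

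**The concern.** An entry limit should not admit a value that the stopping rule already treats as a reason to stop. Here the two meet at one point, 0.03 mg/mg, and the inequality signs differ there.

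The ACR stop is also the least protected of the three renal stops in Section 5.4.3. The creatinine stop requires a persistent elevation with no other cause found, and the urine-blood stop requires a new finding with no other cause found. The ACR stop has no baseline comparison and no alternative-cause clause. The single repeat in Section 5.4 guards against a stray result, but it would confirm a stable baseline value.

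Kidney function is a named area of safety interest in Section 2.2, and each Part 2 cohort has only about 8 active subjects (Section 4.3). A discontinuation caused by an entry value would cost repeat-dose data and could be read as a renal signal.

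**Working it through.** The plan states no figure to reproduce here. The check is a comparison of rules plus a count of infusions.

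**Step 1. Three ACR values around the boundary, put through each rule**

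| ACR (mg/mg) | 5.2 item 19: exclude if >0.03 | 4.6.1: exclude if ≥0.03 | 5.4.3: stop if ≥0.03 |
|---|---|---|---|
| 0.029 | eligible | eligible | continue |
| 0.030 | **eligible** | **excluded** | **stop** |
| 0.031 | excluded | excluded | stop |

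The rules disagree only in the middle row.

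**Step 2. Does another step catch a subject at 0.030?**

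- The second measurement in item 19 applies above the threshold, so it is not triggered.
- The general single repeat in Section 5 is for results that meet an exclusion criterion. Under 5.2 this one does not.
- The recheck in Table 7 note 4 is for a subject who fails on ACR. Under 5.2 this subject does not fail.
- No further ACR is scheduled before dosing.

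**Step 3. How much dosing is at stake in Part 2** (schedule from Section 4.1)

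- Total infusions: 1 (Day 1) + 13 × 3 (Days 2 to 14) + 1 (Day 15) = 41.
- Given before Day 5 dosing: 1 + 3 × 3 = 10. Remaining: 41 − 10 = 31, and 31/41 = 76%.
- Given before Day 15 dosing: 1 + 39 = 40. Remaining: 1.
- Parts 1 and 3 have one infusion, already given by the Day 2 ACR. Remaining: 0.

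The figure of 31 is an upper bound. It assumes that the Day 5 result is reported and repeated before the first Day 5 infusion. The documents give no turnaround time. Each full day needed removes three infusions: one day leaves 28 of 41 (68%), two days leave 25 of 41 (61%).

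**Step 4. How often could it happen?**

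The documents give neither a frequency nor the reporting precision. As an assumption, with rounding to two decimals a measured value from 0.025 to just under 0.035 would print as 0.03; with three decimals, only 0.0295 to just under 0.0305 would print as 0.030. Coarser reporting makes the coincidence more likely, but no rate can be derived.

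**The case against.** **On the ACR boundary.** Section 4.6.1 only outlines the strategy, and its entry lists are shorthand. They differ from Section 5.2 elsewhere too: QTc below 450 msec against an exclusion above 450, and urine negative for blood and protein against an exclusion for blood alone. If 4.6.1 is instead read as binding, a subject at 0.03 faces conflicting rules rather than being plainly admitted. This is fair as far as 4.6.1 goes. It does not remove the mismatch between 5.2 and 5.4.3, which is the one with consequences. Section 5 allows no deviation from the eligibility criteria, so the site needs one unambiguous limit.

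**On a stronger reading.** A reader might infer that the renal pause of Part 1 progression has been lost, because 5.4.3 uses nearly the same findings only to discontinue an individual. The study-level rules are also much coarser. Section 5.4.7 asks for two or more related Grade 3 renal or urinary events. With entry barred for "Serum creatinine >ULN", Grade 3 creatinine needs a rise of at least 3.1 − 1.0 = 2.1 × ULN, or 1.9 to 2.7 mg/dL for an assumed ULN of 0.9 to 1.3 mg/dL, against the 0.3 mg/dL in 4.6.1. That shows 5.4.7 to be a different rule. It does not show that the pause is missing:

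- The pause is written in 4.6.1, and Sections 4.1 and 4.4 both point there for risk mitigation.
- Section 2.2 does not send the reader to 5.4 alone. It assigns the plan for monitoring and managing likely adverse events to 4.6, and withdrawal and stopping to 5.4. Its sentence ends: "the procedures and responsibilities for modifying or stopping the trial, if necessary, are specified in Section 4.6 and Section 5.4, respectively".
- Part 1 ACR, chemistry and urinalysis are scheduled on Day 2, evaluated subjects are followed for at least 48 hours, and all preliminary safety data are reviewed before each escalation (Sections 4.2, 7.1 and 9.3.2).
- Confirmed stopping criteria still require further evaluation under Section 5.4, so 5.4.3 is not empty after a single dose.
- Section 4.6.1 gives no subject count. Reading it as a pause after one subject would add a rule that the protocol does not state.

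**Conclusion.** The ACR inconsistency is real and minor. At exactly 0.03 mg/mg, Section 5.2 lets a subject in, 4.6.1 keeps the subject out, and 5.4.3 takes the subject off drug. The practical exposure is Part 2 Day 5, where an unchanged and confirmed value would end dosing with at most 31 of 41 infusions remaining. On Day 15 one infusion is at stake, and in Parts 1 and 3 none.

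The conclusion rests on the text of the three sections and on screening being the only scheduled ACR before the first dose. It assumes that the site applies the Section 5.2 list literally. How many subjects would be affected cannot be estimated from the documents. Correcting the sign also does not help a subject just under the limit who drifts to it by ordinary variation.

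The documents do not support a claim that the Part 1 renal pause is absent. At most, it would be easier to find if Section 6.3 mentioned it.

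**What to change.** Change Section 5.2 item 19 to exclude an ACR at or above 0.03 mg/mg, and let the second measurement apply to results at or above that value. Sections 5.2, 4.6.1 and 5.4.3 then agree at 0.030.

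The cost is one symbol and a small wording change in an amendment, with no new assessments or visits. The downside is that subjects confirmed at exactly 0.03 are screened out. If the laboratory reports to two decimals, that would include some whose measured value is slightly lower.

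Optional and editorial only: add to Section 6.3 a cross-reference to the renal pause criteria in 4.6.1. It should not add a subject count unless the sponsor decides on one, because 4.6.1 gives none.

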The primary AEs in the 4-week GLP toxicology studies were those at the infusion site. The NOAEL dose in both the rat and monkey for these local infusion site effects (ulcer, perivascular/vascular inflammation, thrombus) was 500 mg/kg; the formulation concentration at this dose was 25 mg/mL for rats and 50 mg/mL for monkeys. These local effects were considered secondary to the high concentrations and resultant high osmolalities of the formulations at doses higher than 500 mg/kg/day. The concentration of the clinical formulation will be limited to no greater than 25 mg/mL (the concentrations at the NOAEL dose for rats), which should preclude these local irritation effects. Based on a concentration limitation of 25 mg/mL, IV solution volumes between 100 to 250 mL would support single doses of 2500 to 6000 mg (IV formulation work is ongoing. Formulation instructions will be available in the Pharmacy Manual before the start of the study) as shown in [Table 2](#).

Table 2 Single IV Infusion Doses, Concentrations, and Osmolality¹

Dose (mg)	Concentration (mg/mL) for a 100 mL infusion	Concentration (mg/mL) for a 250 mL infusion	Final osmolality ² (mOsm/kg)
250	2.5		302
500	5		314
1000	10		339
2000	20		388
4000		16	388
6000		24	407

NOTES:
1. Theoretically calculated osmolality values.
2. Based on 100 mL (250 to 2000 mg doses) and 250 mL (4000 and 6000 mg doses) infusion volumes.

Given that the infusion site reactions can be addressed by formulation, the 2000 mg/kg dose and exposures were selected to define the exposure limits. Slight decreases (10 to 20%) in red blood cell count, hemoglobin, and hematocrit, accompanied by an increase in reticulocytes, as well as other clinical pathology changes considered non-adverse were observed at 2000 mg/kg/day in male and female monkeys; these were considered secondary to the severe and ongoing inflammation induced by the infusion site effects. The hematological findings showed evidence of reversibility by week 4 of dose administration and showed recovery by 4 weeks post dosing. In summary, the hematologic findings were mild, reversible, and able to be monitored in the clinic. The NOAELs of 2000 mg/kg in the rat and monkey with NOAEL exposures of 2875 h•µg/mL (rat) and 2270 µg/mL (monkey) for AUC(0-t) and C_{max}, respectively, were selected to define the exposure limits.

Scaling to human exposure

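### Protocol 4.6.1 relies on normal blood counts and blood pressure at entry, but 5.1 and 5.2 set no limit for them and leave them to investigator discretion

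*Protocol*

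**What the plan says.** The risk table in Protocol 4.6.1 lists these protections at entry:

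- Hematologic findings: "Normal white blood cell (WBC) count, Hgb, Hct, and platelets on study entry".
- Iron binding by the catechol side chain: "Normal Hgb and Hct on study entry".
- The monkey death, and the blood pressure, heart rate and temperature changes: "Normal vital signs on study entry", given in both rows.
- Renal findings: "Urinalysis negative for blood/protein", together with limits on creatinine, eGFR and albumin to creatinine ratio (ACR).

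The eligibility rules are in 5.1 (inclusion 1 to 6) and 5.2 (exclusion 1 to 26). None sets a limit on WBC, Hgb, Hct, platelets, or systolic or diastolic pressure. Inclusion 2 asks a physician to judge the subject healthy. It allows a clinical abnormality or out-of-range laboratory value only where the investigator documents two things: that it is unlikely to add risk factors, and that it will not interfere with procedures. Section 5 forbids deviations from the criteria and allows one repeat of an excluding laboratory test.

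The on-study stops are in 5.4. They include Hgb at or below 9.9 g/dL (5.4.2), and systolic pressure above 160 or diastolic above 100 mm Hg for more than an hour (5.4.5).

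**The concern.** A reader of the risk table would take normal counts and normal blood pressure to be conditions of entry. The table's other entry protections were turned into listed criteria: ALT, bilirubin, QTc, creatinine, eGFR, ACR and urine blood all appear in 5.2. The liver row is phrased in the same way as the hematologic row, and it became a firm ALT limit in exclusion 1. The blood counts and blood pressure were not carried across.

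The Hgb and blood pressure stops are fixed values, not changes from baseline. A subject who starts near one can be exposed to a first-in-human drug and then stopped after a small change. This matters most in Part 2, with 41 infusions per subject. Ordinary study blood sampling, which Section 7 caps at 500 mL, is a further, non-drug reason for Hgb to drift down.

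**Working it through.** The plan gives no figure to reproduce here, so the check is a comparison of sections followed by some headroom arithmetic.

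**Step 1. Entry protection, entry criterion and stop.**

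| Parameter | 4.6.1 at entry | Listed limit in 5.2 | Stop in 5.4.1 to 5.4.5 |
|---|---|---|---|
| ALT | normal | item 1 | ≥3×ULN |
| Creatinine | not above ULN | item 17 | rise >0.3 mg/dL |
| ACR (mg/mg) | excluded at ≥0.03 | item 19, excluded at >0.03 | ≥0.03 |
| Urine blood | negative | item 20 | new blood |
| QTc (msec) | <450 | items 3 and 26 | >500, or change >60 |
| Heart rate | normal | item 26, ≤100 bpm | >120 bpm for >1 hour |
| Hgb | normal | none | ≤9.9 g/dL |
| WBC, platelets | normal | none | absolute lower values |
| Systolic, diastolic BP | normal | none | >160, >100 mm Hg for >1 hour |

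Hct is also listed as normal at entry and has neither a limit nor a stop. Exclusion 6 removes febrile illness. Exclusion 4 does not fill the gap: it rests on investigator opinion and names no hematologic condition.

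**Step 2. Hgb headroom.** The percentage fall needed to reach the stop is (entry − 9.9)/entry.

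- 10.0 g/dL: 0.1/10.0 = 1.0%. 10.5 g/dL: 0.6/10.5 = 5.7%. Both values lie in DMID Grade 1 (9.5 to 10.5, Appendix 6).
- With an assumed lower limit of normal of 11.5, 12.0 or 13.5 g/dL (the documents give none), the fall needed is 13.9%, 17.5% or 26.7%.
- Conversely, a fall of proportion f reaches the stop from 9.9/(1 − f). That is 11.0 g/dL for 10% and 12.4 g/dL for 20%, the range reported in monkeys.

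A normal-range rule therefore removes the closest starters but does not guarantee room for a 20% fall: 12.0 × 0.8 = 9.6.

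**Step 3. Vital-sign margins.**

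- Heart rate: 120 − 100 = 20 bpm, which exceeds the monkey result ("Maximum excursion of 16 beats per minute at 1000 mg/kg").
- Blood pressure: there is no entry cap, so the margin can be near zero. Illustrative caps of 140/90 and 130/85 would give 160 − 140 = 20 and 100 − 90 = 10, or 30 and 15 mm Hg. The monkey result was "Maximum excursion of 29 mm Hg at 1000 mg/kg", with no direction stated.

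**Step 4. How far the animal figures carry.** The Hgb fall occurred at 2000 mg/kg/day and was attributed mainly to infusion-site inflammation, with a contribution from high osmolality. Protocol 4.5 addresses this: "The concentration of the clinical formulation will be limited to no greater than 25 mg/mL". For blood pressure, 4.6.1 puts Cmax at 6000 mg at 1.1 times that of the 250 mg/kg no-effect dose. Scaling by the Appendix 9 medians to the Part 2 maximum of 4000 mg gives 1.1 × 437/657 = 0.73. The animal changes serve as yardsticks, not as predictions of human effects.

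**Step 5. Size of the loss.** Part 2 gives 1 + 13 × 3 + 1 = 41 infusions. An avoidable stop there costs 1 of about 8 active Day 15 profiles in a cohort, unless the subject is replaced (4.3).

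**The case against.** The strongest reply is that the protection exists. Inclusion 2 requires a physician's finding of health and a documented reason for any exception. An investigator whose protocol names normal Hgb as a mitigation for this drug would find it hard to justify admitting a Grade 1 value, or a resting pressure near 160/100. That stands, and it is why the gap is one of discretion rather than absence.

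A reader might infer that only 5.1 and 5.2 bind, so that enrolling such a subject could never breach the protocol. The documents do not settle this. Section 5 forbids deviations from the criteria but does not make the rest optional. Section 7 requires adherence to the study design requirements, and 2.2 and 4.4 send the reader to 4.6 for monitoring and mitigation.

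A reader might also count 11 parameters with a stop in 5.4.1 to 5.4.5, note that 6 have an entry limit and 5 do not, and treat this as a broken pairing rule. The count is right, but the creatinine and urine-blood stops concern change or new findings, so their entry limits are not headroom against a fixed value. The comparison bears mainly on Hgb and blood pressure. WBC and platelets matter less, since the risk table reports no fall in either.

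The confirmatory repeat for laboratory stops (5.4) and the one-hour condition for blood pressure also keep transient readings from triggering a stop. In Parts 1 and 3 a later laboratory stop cannot undo a single completed infusion.

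**Conclusion.** The mismatch is real. Section 4.6.1 states normal blood counts and vital signs at entry as mitigations, while 5.1 and 5.2 leave blood counts and blood pressure to documented judgement. Within the vital signs, heart rate and febrile illness are covered.

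The consequence is modest and falls mainly in Part 2: a borderline volunteer may be exposed and then stopped after a small change. A reader might go further and expect confounded results or blocked escalation. Neither follows. Baseline is the latest pre-dose value (SAP 10.3.2.1) and change from baseline is tabulated. Reticulocytes and iron tests are repeated on Days 5 and 15. Part 2 placebo is reported as one group of about 3 × 2 = 6 subjects. Escalation needs about 5 of about 8 active subjects.

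The percentages in Step 2 rest on assumed lower limits of normal, and the blood pressure margins on illustrative caps. The textual gap depends on neither. The change is recommended rather than essential.

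Separately, an ACR of exactly 0.03 mg/mg is eligible under exclusion 19 yet already meets the 5.4.3 stop. The urine-protein difference (4.6.1 names blood and protein, exclusion 20 only blood) is a matter of alignment: exclusion 19 screens for raised ACR and 5.4.3 has no dipstick-protein stop.

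**What to change.** Amend Protocol 5.2 as follows:

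- Exclude Hgb, Hct, WBC or platelets outside the laboratory reference range, with the one repeat that Section 5 already allows.
- Exclude resting systolic or diastolic pressure outside a sponsor-defined normal range. Set both upper and lower limits, with the upper well below 160/100 mm Hg. A lower limit is needed because 4.6.1 says normal and 5.4.7 has a low-pressure criterion.
- State that inclusion 2 discretion does not apply to these parameters.
- Change exclusion 19 from >0.03 to ≥0.03 mg/mg.
- For alignment, add protein to exclusion 20 or reword 4.6.1 to rely on the ACR.

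No new tests are needed: hematology, urinalysis and vital signs are already done at Screening and Day −1 (Table 3).

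The cost is extra screen failures. Assume that each reference limit cuts off 2.5% of healthy people, so each two-sided range cuts off 5%. The four blood tests then exclude between 5% (fully correlated) and 1 − 0.95⁴ = 18.5% (independent) per visit, before the repeat.

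- For 30 Part 2 places: 30/0.95 − 30 = 1.6 to 30/0.815 − 30 = 6.8 extra people screened.
- For all 48 + 30 + 10 = 88 places: 4.6 to 20.0.

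Hgb and Hct move together, so the independent figure is an upper bound; some of these people would also be turned away under inclusion 2 today. Limiting the exclusion to low values would roughly halve the cost (1 − 0.975⁴ = 9.6% at most, or 0.8 to 3.2 extra for Part 2), but would not deliver the normal counts that 4.6.1 states. The blood pressure share depends on the range chosen.
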